#### **Projected Overall Study Timeline**

	Study Start-Up	Enrollment	Data Entry and Analysis	Study Write-Up
MM YYYY	06 2010			
MM YYYY		07 2010		
MM YYYY			07 2012	
MM YYYY				07 2012

# 9.0 CONCOMITANT THERAPIES Not applicable

#### 10.0 DRUG INFORMATION

The risks associated with IV ketamine when used alone at doses of 1-4 mg/kg include emergence reaction. Medication package insert includes a black box warning listing: "incidence of 12%; psychological manifestations vary in severity between pleasant dream-like states, vivid imagery, hallucinations, and emergence delirium; may be assoc. w/ confusion, excitement, and irrational behavior; duration usually a few hours, recurrences up to 24h post-op in few cases; no residual psychological effects; decr. incidence in <15 y/o and >65 y/o, if IM dose, or previous exposure; decr. incidence w/ lower doses in combo w/ diazepam during

anesthesia induction and maintenance; use small hypnotic dose of shortor ultrashort-acting barbiturate to end severe emergence rxn

Other possible severe adverse reactions include: respiratory depression, laryngospasm, ICP incr., IOP incr., hypotension, severe, bradycardia, arrhythmias, delirium, hallucinations, tonic clonic movements, anaphylaxis, withdrawal syndrome (long-term use).

Other common adverse reactions include: hypersalivation, anorexia, nausea/vomiting, elevated BP, elevated HR, diplopia, nystagmus, fasciculations, depressed reflexes, hallucinations, bradycardia hypotension.

Ketamine is contraindicated or should be used with caution if patients with: hypersens. to drug/class/compon., HTN, stroke, head trauma, intracranial mass/hemorrhage, caution if ICP incr., caution if IOP incr., caution if CAD, caution if CHF, caution if thyrotoxicosis, caution if psychosis, caution if hepatic impairment, caution if acute alcoholism, caution if chronic alcohol use, caution if substance abuse, caution in elderly pts. < www.epocrates.com>

Other severe side effects are rare and are typically reversible with cessation of drug infusion. Common side effects are also typically reversible with cessation of infusion. Multiple studies have demonstrated that low-dose ketamine, when given with anesthetic induction agents and inhalational anesthetic gas, is safe and effective with few if any, adverse side effects. <Bell RF, Cochrane Review, 2005>

Investigational New Drug (IND) Application Required?: No

# 11.0 STATISTICAL CONSIDERATIONS

Statistical analysis with *a priori* power analysis was performed to determine the number of patients per group sufficient to detect a decrease of >30% in postoperative opioid requirements on the basis of the results of Kararmaz et al., Anesthesia and Analgesia 2003. With a power of 80% and a type 1 error of 5%, it was estimated that 32 patients will be required per group. We will plan to enroll 65 patients total to account for unanticipated subject dropout. Mann-Whitney U-test will be used to compare VRS, modified Aldrete, and patient satisfaction scores. Student's t-test will be used to compare BMI, time to first analgesic, number of analgesic demands, amount of analgesic consumption and ODI. The X2 test will be used to compare frequency of side effects, race and sex distribution. The resulting values will be expressed as mean +/- SD or median and range with P< 0.05 considered statistically significant.

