#### 6.0 ELIGIBILITY & EXCLUSION CRITERIA

Inclusion criteria: Total of sixty-five patients, aged 19-70, scheduled to undergo laparoscopic gastric bypass surgery for morbid obesity. Patients should have a diagnosis of obstructive sleep apnea as confirmed by sleep study and are not currently using a CPAP devise. If no sleep study is available, patients should have the 4 clinical predictors of obstructive sleep apnea as described by STOP (Snoring, Tiredness during daytime, Observed apnea, high blood Pressure) screening questionnaire. <Chung, F Anesthesiology 2008>

Exclusion criteria: Patients <19 yrs, positive pregnancy test, ASA> III, history of alcohol or narcotic abuse in last 90 days, significant cardiovascular or respiratory disease (baseline oxygen saturation below 92%), significant psychiatric or neurologic disease, history of significant hepatic or renal disease (baseline creatinine>1.5), history of allergy or contraindication to anesthetic agents or ketamine including patients with increased ICP, increased IOP, severe arrhythmias, history of delirium, hallucinations, or psychosis, or history of uncontrolled seizures, or potential risk for malignant hyperthermia (family history), history of difficult intubation that would preclude standard induction of anesthesia, prisoners, persons who are mentally impaired, and non-english speakers.

Criteria for early withdrawal for the study: <2 hrs surgical time, any surgical or anesthetic complication that prevents the assessment of study variables, clinically relevant residual neuromuscular blockade or other reason for patient to require prolonged tracheal intubation following surgery.

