#### 15. Participants (Screening and Selection)

- a. How many participants are to be enrolled at UAB?  $\underline{150}$  If multi-center study, total number at all centers:  $\underline{N/A}$
- **b.** Describe the characteristics of anticipated or planned participants.

Sex: Male or Female

Race/Ethnicity: All representative of patients undergoing general ENT or Orthopedic surgery; Expand the patient population to include all patients undergoing surgery requiring to general anesthesia due to the limited amount of patients that are able to be recruited.

Age: 18-100

Classification of 1-3 and who are morbidly obese patients with obstructive sleep apnea scheduled general ENT or Orthopedic surgery. ASA Classification of 1 = A normal healthy patient, ASA Classification of 2 = A patient with mild systemic disease (examples: current smoker, social alcohol drinker), ASA Classification of 3 = A patient with significant systemic disease (examples: Poorly controlled diabetes or hypertension), and ASA Classification of 4 = A patient with severe systemic disease that is a constant threat to life (examples: MI, CVA, TIA, or CAD/stents, ongoing

cardiac ischemia or severe valve dysfunction, severe reduction of ejection fraction, sepsis, DIC, ARD or ESRD not undergoing regularly scheduled dialysis).

Note. If data from prior studies indicate differences between the genders or among racial/ethnic groups in the proposed research or if there are no data to support or to negate such differences, Phase 3 clinical trials will be required to include sufficient and appropriate entry of gender and racial/ethnic subgroups so that trends detected in the affected subgroups can be analyzed. If ethnic, racial, and gender estimates are not included in the protocol, a clear rationale must be provided for exclusion of this information. If prior evidence indicates that the results will not show gender or racial differences, researchers are not required to use gender or race/ethnicity as selection criteria for study participants. They are, however, encouraged to include these groups. See Section II. Policy of the NIH POLICY AND GUIDELINES ON THE INCLUSION OF WOMEN AND MINORITIES AS SUBJECTS IN CLINICAL RESEARCH – Amended, October, 2001) for further details.

C. From what population(s) will the participants be derived?
The study population will be derived from those patients who are morbidly obese scheduled to undergo general ENT and orthopedic surgery.

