Describe your ability to obtain access to the proposed population that will allow recruitment of the necessary number of participants:
All patients scheduled for the above surgical procedure will be seen preoperatively in the PAC at TKC and Highlands. The opportunity to participate will be offered at such time.

Describe the inclusion/exclusion criteria:

Inclusion criteria: aged 19-100, scheduled to undergo general ENT or Orthopedic Surgery.

Patients should have a diagnosis of obstructive sleep apnea as confirmed by sleep study or deemed high risked for obstructive sleep apnea by clinical predictors (greaterthan 4 clinical predictors of obstructive sleep apnea as described by STOP BANG).

Exclusion criteria: positive pregnancy test, ASA> III, history of alcohol or narcotic abuse in last 90 days, significant cardiovascular or respiratory disease (baseline oxygen saturation below 92%), significant psychiatric or neurologic disease, history of significant hepatic or renal disease (baseline creatinine>1.5), history of allergy or contraindication to anesthetic agents or ketamine including patients with increased ICP, increased IOP, severe arrhythmias, history of delirium, hallucinations, or psychosis, or history of uncontrolled seizures, or potential risk for malignant hyperthermia (family history), history of difficult intubation that would preclude standard induction of anesthesia, prisoners, persons who are mentally impaired, and non-English speakers.

- **d.** If participants will comprise more than one group or stratification, describe each group (e.g., treatment/intervention, placebo, controls, sham treatment) **and** provide the number of participants anticipated in each group.

  Participants will be randomly assigned to either the low-dose Ketamine infusion group or the normal saline infusion group. The two groups will comprise the study population, n=150.
- e. Indicate which, if any, of the special populations listed below will be involved in the protocol. Include the Special Populations Review Form (SPRF) if indicated.

  □ Pregnant Women: Attach SPRF—Pregnant Women, Fetuses, Neonates/Nonviable Neonates

□ Fetuses: Attach SPRF—Pregnant Women, Fetuses, Neonates/Nonviable
Neonates
□ Neonates/Nonviable Neonates: SPRF—Pregnant Women , Fetuses ,
Neonates/Nonviable Neonates
□ Prisoners: Attach SPRF—Prisoners
☐ Minors (<18 years old): Attach SPRF—Minors
⋈ Employees or students at institution where research conducted

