#### 23. Additional Information

In the space below, provide any additional information that you believe may help the IRB review the proposed research, or enter "None."

This study was originally closed on May 28, 2014. The PI is now requesting to re-open this protocol. The PI understands that it has been over a year and will have to re-submit the protocol. You will find attached the originally approved HSP. A few personnel were added and removed along with changes to the patient population (now focusing on patients undergoing general ENT or Orthopedic surgery).

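### The only stated sample size and power (32 per group, 65 enrolled) do not describe the re-opened study of 150, and the powered opioid outcome is neither named primary nor tied to one window

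*Combined protocol and SAP*

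**What the plan says.** **Size and power.** Sections 5.0 and 11.0 of the protocol (version 11/16/09) carry the same power statement, for a decrease of more than 30% in postoperative opioid requirements: "With a power of 80% and a type 1 error of 5%, it was estimated that 32 patients will be required per group". Both continue: "We will plan to enroll 65 patients total to account for unanticipated subject dropout". Section 6.0 ties that number to one operation: "Total of sixty-five patients, aged 19-70, scheduled to undergo laparoscopic gastric bypass surgery for morbid obesity".

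**The re-opened study.** Item 23 of the human subjects form says the study was closed in May 2014 and that "The PI is now requesting to re-open this protocol". It lists changes to personnel and to the patient population; sample size is not among them. Item 15.a gives 150 participants, and item 15.d says "The two groups will comprise the study population, n=150". Item 15.d also asks for the number in each group, and none is given.

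**The new population.** Item 15.b gives ages 18-100 and describes morbidly obese patients having general, ENT or orthopedic surgery, but also says "Expand the patient population to include all patients undergoing surgery requiring to general anesthesia". Item 15.c says "The study population will be derived from those patients who are morbidly obese scheduled to undergo general ENT and orthopedic surgery". The inclusion criteria that follow give ages 19-100 and general ENT or orthopedic surgery, with no obesity criterion.

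**Outcomes.** Section 11.0 assigns tests to eight postoperative outcomes: pain score (VRS), modified Aldrete score, satisfaction, time to first analgesic, number of demands, analgesic consumption, oxygen desaturation index and side effects. It closes with "The resulting values will be expressed as mean +/- SD or median and range with P< 0.05 considered statistically significant". No outcome is called primary. The opioid outcome appears as supplemental intravenous morphine (Section 4.0 and item 13), as analgesic consumed in the operating room (OR) and PACU (Section 8.0), and as morphine usage assessed at 24 hours (Section 8.0).

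**The concern.** A power statement should tell the reader what the trial, as it will be run, can detect. Here the only one available was written for 65 gastric bypass patients, while the study to be run has 150 patients having other operations. The documents give no mean, SD, sidedness, allocation ratio or expected withdrawal fraction for either version. Losses are foreseeable: item 19.b withdraws patients for surgery under two hours, for complications that prevent assessment, and for prolonged intubation. The power cannot be restated until the form's own population statements agree, because the variability of opioid use depends on who is enrolled.

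The second problem does not depend on the number enrolled. With eight outcomes each judged at 5%, no primary, and the powered outcome open to more than one window, whichever result crosses the threshold could become the main claim after the data are seen. The main claim would then not be held at 5%.

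**Working it through.** **Inputs from the documents.** 32 per group; 80% power; type I error 5%; 30% relative decrease; Student's t-test for analgesic consumption (Section 11.0); 150 participants (items 15.a and 15.d); eight postoperative outcomes at P<0.05 (Section 11.0).

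**Assumptions, because the documents are silent.** Two-sided test, 1:1 allocation, equal SDs, and 30% loss as an illustration. The correlations between outcomes are also assumed.

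**1. What 32 per group implies.** The figure cannot be reproduced forwards, since no SD or CV is given. Solving the noncentral t backwards for 80% power with 32 per group gives a standardized difference d = 0.711. For a 30% decrease, CV = 0.30 / 0.711 = 0.422. So 32 per group is attainable if the CV is about 42%, but it cannot be verified.

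**2. What 150 gives at that CV.** Here 42% is taken as the total CV, with no adjustment for surgery type. The detectable decrease is the d detectable at 80% power times 0.422. The CV limit is 0.30 divided by the same d.

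| Evaluable | Per group | Power for 30% | Detectable d at 80% | Detectable decrease | CV limit for 80% power |
|---|---|---|---|---|---|
| 150 | 75 | 99.1% | 0.460 | 0.460 x 0.422 = 19.4% | 0.30 / 0.460 = 65% |
| 105 (30% loss) | 52.5 | 95.1% | 0.552 | 0.552 x 0.422 = 23.3% | 0.30 / 0.552 = 54% |

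**3. If mixed surgery is more variable.** With 150 evaluable and CV 70%, d = 0.30 / 0.70 = 0.429 and power is 74%. With 105 evaluable and CV 60%, d = 0.30 / 0.60 = 0.50 and power is 72%.

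**4. Eight tests at 5%.** If independent, the chance of at least one false positive is 1 - 0.95^8 = 0.337. For equally correlated normal statistics, simulation gives 0.30, 0.25, 0.19 and 0.12 at correlations 0.3, 0.5, 0.7 and 0.9.

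**5. Two windows for opioid use (PACU or 24 hours).** If the better of two correlated two-sided tests is reported, simulation gives 0.09, 0.08 and 0.07 at correlations 0.5, 0.7 and 0.9, against 0.05 with one window fixed.

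**The case against.** The strongest reply is that the two sizes belong to two stages of one study, so they do not collide within a single text, and that a larger trial can only help. The first half is fair: 65 comes from the 2009 gastric bypass protocol and 150 from the later form. But nothing withdraws or updates Section 11.0, item 23 does not list sample size among the changes, and the form as supplied has no statistical section of its own. If Section 11.0 were treated as superseded, the re-opened study would have no tests, error rate or power at all in the text available. Some pages were not available for this review, so the absence of a basis for 150 is shown only for the text that was.

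The second half is right at the implied CV, where 150 is ample. A reader might infer that the re-opened study is underpowered, or that 32 is a wrong calculation; the documents support neither. Equally, they do not support saying that 150 is certainly enough, because the CV in mixed surgery is unknown.

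Two other readings are tempting. Item 16 does not mention opioid use in its account of what will be compared, from which a reader might infer that the form dropped the outcome. Item 16 is a lay summary and its list is not exhaustive, and item 13 of the same form names both opioid requirements and supplemental morphine. A reader might also infer that discretionary OR fentanyl dilutes the powered comparison. Section 11.0 powers on postoperative opioid, and the Section 8.0 wording can be read as two separate amounts. Any figure for the loss of power would need a ratio of OR to postoperative use that the documents do not give.

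**Conclusion.** The point stands, in two parts.

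First, the stated size and power describe a 65-patient gastric bypass study, not the 150-patient study being re-opened, and the new population is itself described inconsistently. Taken alone this is a fault of documentation: power for a 30% decrease falls below 80% only if the CV exceeds 65% with 150 evaluable, or 54% with 105. Those limits rest on a two-sided test, equal allocation and equal SDs, and the 105 rests on an assumed 30% loss.

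Second, and more serious for what can be concluded, no outcome is primary and the powered one has no single window. The chance of at least one false positive across the eight outcomes is 12% to 34%, depending on correlation. It is 7% to 9% from the choice of opioid window alone, for correlations of 0.9 down to 0.5. This needs correcting before the analysis, whatever the number enrolled.

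**What to change.** **(a) Size and population.** Reconcile items 15.b and 15.c and the inclusion criteria with one another on age, obesity and type of surgery. Then bring Sections 5.0, 6.0, 7.0 and 11.0 into line with them. Replace the 65-patient power statement with the power, or the detectable decrease, for the evaluable part of 150, and state the assumed mean, SD, sidedness, allocation ratio and withdrawal fraction. If the CV judged realistic for the new population gives less than 80% power for a 30% decrease, state the lower power or the larger detectable decrease.

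**(b) Outcome.** Name postoperative opioid requirement from PACU arrival to 24 hours, in one opioid unit, as the single primary outcome tested at 5%. Section 8.0 already assesses morphine usage at 24 hours. Report OR opioid separately, PACU use as secondary, and the other outcomes as secondary and supportive only. This protects the primary claim; it does not lower the 12-34% across all eight tests.

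**Cost.** Mostly wording and one recalculation. Secondary claims become weaker. Any non-morphine opioid must be recorded and converted, since item 16 leaves postoperative pain medication to current practice.

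**Optional.** Adjusting the opioid comparison for surgery type could recover precision. If that is shown in the power statement, the 42% must be labelled as the CV within surgery type, not the total CV used above.

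### The 65-patient target allows for the loss of one patient (1.5%), although the protocol mandates several kinds of withdrawal, and it is not reconciled with the 150 in the re-opened application

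*Combined protocol and SAP*

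**What the plan says.** Section 11.0, repeated in section 5.0, sizes the trial on postoperative opioid requirement, to be "sufficient to detect a decrease of >30% in postoperative opioid requirements". The result is: "With a power of 80% and a type 1 error of 5%, it was estimated that 32 patients will be required per group". The next sentence sets enrolment: "We will plan to enroll 65 patients total to account for unanticipated subject dropout". Section 6.0 repeats the total of sixty-five.

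The withdrawal rules are in three places:

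- Section 6.0: "Criteria for early withdrawal for the study: <2 hrs surgical time", then complications that make the study variables impossible to assess, and residual neuromuscular blockade or another cause of prolonged intubation.
- Section 13.0: the same complications, blockade and intubation, plus any surgical or anesthetic complication that makes it necessary to depart from routine anesthetic management. Short surgery is not mentioned here.
- Item 19.b of the re-opened Human Subjects Protocol: the section 6.0 list again, including short surgery.

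None of these places says whether a withdrawn patient is replaced or stays in the analysis. Items 15.a and 15.d of the re-opened application give enrolment as 150 for the two groups together, with no power calculation and no dropout allowance.

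**The concern.** The enrolment sentence claims that dropout has been provided for, and the figure beside it provides for almost none. The mandated withdrawals depend on events that follow allocation: length of surgery, complications, residual blockade, delayed extubation. They are losses after randomisation, not screening failures, and more than one of them in 65 patients is foreseeable.

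If the 65-patient plan is the one cited, a non-significant opioid result could be presented as coming from a trial that kept 80% power after dropout, when the plan contains no such margin. The second target of 150 makes this harder to judge, because a reader cannot tell which number the power statement belongs to.

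**Working it through.** **Inputs**

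- From section 11.0: 32 per group, 80% power, 5% type 1 error, Student's t-test for analgesic consumption, 65 enrolled.
- From items 15.a and 15.d of the re-opened application: 150 enrolled.
- Assumed because not stated: two-sided test, 1:1 allocation, withdrawn patients leave the analysis, and every withdrawal rate used below.

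**1. The plan's own figure.** The 32 per group cannot be reproduced, because the documents give neither a control mean nor an SD. They refer to an earlier ketamine trial whose results they do not show. The effect can be solved backwards:

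- Normal approximation: d = (1.960 + 0.842) × √(2/32) = 0.700.
- Two-sample t-test (noncentral t): d = 0.711.

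For a 30% decrease this implies an SD of 0.30/0.711 = 0.42 of the control mean. The calculation is coherent at that value, so 32 per group is taken as given.

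**2. The allowance.** 65 − 2 × 32 = 1 patient, and 1/65 = 1.54%.

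**3. Power as patients are lost from 65.** This uses the t-test at d = 0.711. As a hand check, power ≈ Φ(0.700/√(1/n₁ + 1/n₂) − 1.960). For 26 + 26 that is Φ(2.525 − 1.960) = 71.4%, against 71.1% from the t-test.

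| Evaluable | Lost | Power |
|---|---|---|
| 65 (33 + 32) | 0 | 80.6% |
| 64 (32 + 32) | 1 | 80.0% |
| 63 (32 + 31) | 2 | 79.3% |
| 60 (30 + 30) | 5 | 77.3% |
| 58.5 expected (10% assumed) | 6.5 | 76.3% |
| 52 (26 + 26; 20% assumed) | 13 | 71.1% |

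**4. How likely a second loss is.** With 65 patients and withdrawal probability p, P(at least 2) = 1 − (1 − p)⁶⁵ − 65p(1 − p)⁶⁴. This gives 58% at p = 3%, 84% at 5% and 99% at 10%. The documents give no value for p.

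**5. The 150 target at the same effect.**

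- 75 + 75 evaluable: 99.1%.
- 20% withdrawn, 60 + 60 evaluable: 97.2%.
- Loss that would still leave 64 patients: 1 − 64/150 = 57%.

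These figures carry over the effect implied for laparoscopic gastric bypass. Items 15 and 23 of the re-opened application change the population to general, ENT or orthopedic surgery, and item 15.b widens it to any surgery under general anesthesia. No calculation shows that the same effect and variability apply there.

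**The case against.** The strongest reply is that the re-opened application enrols 150. If the effect behind 32 per group still holds, 150 absorbs any plausible attrition and the harm from dropout disappears. That stands for a trial that reaches 150 under that effect, and it confines the power shortfall to the 65-patient plan. It does not repair the sentence in sections 5.0 and 11.0, which remain the only sample-size justification in the file, and it leaves two enrolment targets side by side.

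It is also fair to say that withdrawn patients might still be analysed. A patient withdrawn for short surgery could have complete PACU opioid data, and power would then not fall. No analysis set is defined, so this is open, and the loss must be stated as conditional.

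A reader might infer more than the documents support:

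- *That the 80% power is lost at the second withdrawal.* It crosses below 80%, but only to 79.3%. A material fall needs attrition of roughly 10 to 20%, and those rates are assumptions.
- *That the plan promises 80% power after dropout.* It attaches 80% to 32 per group. What it claims about dropout is only that 65 allows for it.
- *That every departure from routine anesthetic management leads to removal, or that withdrawal will be routine.* Section 13.0 covers only departures made necessary by a complication. The listed events are mandatory grounds for withdrawal, but no frequency is given for any of them.

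**Conclusion.** The point holds in a limited form. As written, the dropout allowance is one patient in 65 (1.5%), with no stated rate and no replacement rule, beside rules that mandate withdrawal for several events after allocation. The cost in power is slight for a few losses and moderate at 10 to 20%, where it is about 4 to 9 percentage points below the stated 80%. That size rests on a two-sided test, 1:1 allocation, an effect solved backwards from 32 per group, and withdrawn patients leaving the analysis.

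It would go too far to call the re-opened trial underpowered because of dropout: 150 patients at the implied effect would have ample power. For 150 the defect is different. The number has no calculation behind it, and it is not reconciled with 65.

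**What to change.** 1. In sections 5.0 and 11.0, replace the dropout claim with wording such as: *Enrolling 65 patients keeps 80% power only if at most one patient is lost. If withdrawn patients are not analysed, power is about 76% with 10% withdrawn and 71% with 20%; these rates are assumptions.* Add the two-sided 5% level if that is what was used.
2. State whether withdrawn patients are replaced and whether they remain in the analysis.
3. Reconcile the 65 in sections 5.0, 6.0 and 11.0 with the 150 in items 15.a and 15.d, and state which target governs. For that target, give the number expected to be evaluable after withdrawals and the resulting power, with the mean and SD assumed for the current surgical population.

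The cost is a few sentences in the protocol and one or two in the re-opened application. The stated power of the 65-patient plan becomes slightly less favourable. No increase in enrolment and no change to clinical conduct is asked for.
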